Appendix F. Antibody, Antigen, and viral RNA Assays and Outcomes

SARS-CoV-2 antibody and antigen levels were measured in plasma specimens collected at baseline (Day 0), Day 1, Day 3, and Day 5. Antibody and antigen levels were determined centrally, by the Frederick National Laboratory, blinded to treatment group.

Antibody Levels

SARS-CoV-2 plasma antibody levels were measured using two assays:

- Levels of neutralizing antibodies (nAbs) directed against the SARS-CoV-2 receptor binding domain (RBD) were determined using the GenScript SARS-CoV-2 Surrogate Virus Neutralization Test (sVNT) assay (GenScript, Piscataway, NJ, USA).
 - Levels of nAbs reported as "percent binding inhibition". Specimens with levels <30% are considered nAb negative, levels
 30% are considered positive for nAbs (30% is the manufacturer's cutoff for positivity).
- **BioRad** Platelia SARS-CoV-2 Total Ab assay (BioRad, Hercules, CA, USA), measuring total (IgA, IgG, and IgM) anti-nucleoprotein (**Anti-N**) antibodies.
 - Results of this antibody measurement are reported as "specimen ratios". Specimen ratios are defined as the specimen optical density (OD) divided by the optical density of the cut-off control R4 (OD_MR4). According to the manufacturer, specimen ratios less than 0.8 are considered negative, those with a specimen ratio between 0.8 and 1.0 are considered equivocal, and those > 1.0 are considered positive for the presence of antibodies.
 - Equivocal BioRad antibody levels will be combined with negative levels for all analyses unless otherwise stated.
- **Quanterix** anti-Spike IgG semi-quantitative antibody assay (Simoa® Semi-Quantitative SARS-CoV-2 IgG Antibody Test, Quanterix, Bellerica, MA, USA).
 - Automated paramagnetic microbead-based immunoassay intended for qualitative and semi-quantitative detection of IgG antibodies to SARS-CoV-2 in human dipotassium EDTA plasma using the Quanterix HD-X immunoassay system.
 - Functional LLoQ of 82 ng/mL
 - Antibody-positive defined as > 770 ng/mL per manufacturer's recommendation ("clinical cut-off")
 - The performance of the assay has not been established in individuals that have received a COVID-19 vaccine

Comment: For the purpose of comparing natural immunity and whether nMAbs have potential benefit in those with such, the GenScript assay will be used. This attempts to quantify neutralizing antibody titers, whereas the BioRad assay captures any type of anti-N antibody (against a section of virus not causing neutralization).

Plasma Antigen Levels

SARS-CoV-2 nucleocapsid antigen levels were determined in 90 µL plasma in duplicate using

a **Quanterix** assay (Simoa® SARS-CoV-2 N Protein Advantage, Quanterix, Bellerica, MA, USA). The lower limit of quantification for the assay is 3 ng/L.

 \circ Antigen levels < 3 ng/L are considered "antigen negative".

Comments:

- When analyzed as continuous variable, Quanterix antigen levels <3 will be set to 2.9 ng/L.
- When analyzed as continuous variable, antigen levels will be log₁₀-transformed.

SARS-CoV-2 Viral RNA was assessed at baseline from mid-turbinate nasal swabs.

Qualitative and quantitative assessments of the SARS-CoV-2 RNA in viral transport media (proxy for viral load) by RT-PCR were made centrally by ABML.

- Qualitative RT-PCR analysis: Extraction, master mix preparation, and RT-PCR were performed as described in the CDC 2019-Novel Coronavirus Real-Time RT-PCR Diagnostic Panel. RT-PCR was performed on an Applied Biosystems QuantStudio 7 Flex. Ct scores <40 for both nCoV N1 and nCoV N2 probe sets are scored as positive for the presence of SARS-CoV-2 RNA.
- *Quantitative RT-PCR analysis:* Quantitative RT-PCR analysis of the samples used the same RNA extracts prepared for the qualitative assay. Assay conditions were the same as outlined in the CDC protocol except the RNaseP probe was not used.

Comments:

- For subgroup analyses, RNA levels in viral transport media will be categorized as (<10,000 cp/mL [low] versus >10,000 cp/mL [high]); the cut-point is close to the median viral RNA level in the TICO bamlanivimab trial. Indeterminate levels will usually be combined with negative levels for analyses.
- \circ When analyzed as continuous variable, RNA levels will be log₁₀-transformed.

Appendix G. Modifications to the Statistical Analysis Plan for MP0420

Investigational Agent

Appendix H5, version 2.0 (09 April 2021) of the TICO protocol describes agent-specific protocol elements for MP0420 which is being developed by Molecular Partners and Novartis. MP0420 is multi-valent DARPin® molecule consisting of 5 DARPin® domains. MP0420 simultaneously and specifically binds to 3 epitopes of the receptor-binding domain of the SARS-CoV-2 spike protein with three different domains and to human serum albumin with two domains.

Analysis Population

Treatment comparisons for efficacy and safety outcomes will be by modified intention-to-treat (mITT). The mITT analysis is restricted to participants who received a complete or partial infusion of MP0420/placebo; participants who did not receive any MP0420/placebo are excluded. The TICO platform protocol specifies ITT for the efficacy analyses "unless otherwise stated", and mITT for safety analyses.

Justification for changing the study population to mITT for efficacy analyses: In the TICO trial of MP0420, 496 participants were randomized (ITT population). Of these, 485 were infused (complete or partial) with MP0420/placebo and 11 were not. Of the 11 participants not infused, 9 withdrew consent prior to infusion. Follow-up data after Day 0 was collected for the 2 participants not infused, but remained consented. Because the treatment assignment was blinded, the risk of bias due to restricting analyses to the mITT cohort is low. With this approach, the risk and benefits of MP0420 will be evaluated in the same population.

Comment: Investigators were unblinded to summaries of the infusion status of participants, pooled across treatment groups. These analyses were included in the open DSMB reports.

Hypersensitivity Events of Special Interest

In October 2021, we were informed of 3 participants who experienced hypersensitivity reactions in a Molecular Partners study of 20 healthy volunteers. The 3 participants received a 400 mg subcutaneous dose of MP0420 and each developed non-serious (mild to moderate) rash and joint/body pain 10 to 20 days after the single subcutaneous infusion. A total of 8 participants received the 400 mg dose in this study.

These cases were discussed on October 20, 2021, at a TICO investigator meeting and are also described in a memorandum from trial leadership to investigators in ACTIV-3 (TICO) on November 2, 2021. At that time we requested that investigators increase vigilance of participants who developed rash and simultaneously joint, muscle, and/or body aches.

On November 5, 2021, revised informed consents and drug information sheets that described these events were sent to sites and to the Advarra central IRB.

On December 7, 2021, all participants for whom rash adverse events had been reported through Day 28 were identified. Sites were asked to complete an eCRF for each event. Eleven participants experienced rash events through Day 28. The number and percentage of participants with a rash event by treatment group will be summarized. Rash events associated with myalgia, arthralgia, or generalized aches and pains will also be summarized by treatment group.

Line listing of events will include severity grade, rash characteristics, location, and other solicited events that occurred simultaneously.

No formal statistical testing will be carried out on the rash events alone. In a supplemental analysis for the Day 28 composite safety outcome which includes deaths, SAEs, organ failure, serious infection and grade 3 or 4 adverse events, the rash adverse events will be included as a separate component.

Subgroup Analyses

In addition to the subgroup analyses described in section 9, those described in section E-7 (vaccine and immunosuppressive status) and E-8 (viral strain) of Appendix E will be carried out for MP0420 for the outcomes listed in section 9.

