# H5.5.4. Adverse Events of Special Interest (AESI)

The following are AESIs for the agent MP0420 or placebo:

- Infusion-related reactions
- Allergic/hypersensitivity reactions

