Some biomarkers will be measured centrally from stored samples, for example, hsCRP, IL-6, D-dimer, SARS-CoV-2 antibody, antigen, and viral RNA levels, and SARS-CoV-2 genome sequencing and variant identification. If these measures are available, they will be included in interim reports.

6 Administration of Study Treatment

These data are an important part of the safety review, with particular emphasis on infusionrelated reactions and symptoms occurring during or within up to 2 hours after the infusion. These reactions and symptoms will be graded according to the DAIDS AE Grading Table.

The administration of study treatment is also an essential element of study conduct. Several summaries, pooled across treatment groups, will be included in the open report or provided to study leadership. Any summaries of adverse events or infusion-related reactions are restricted to the closed report.

For investigational agents administered as a one-time infusion, the following statistics will be used to summarize the infusion in each treatment group (active and control):

- Number and percentage of participants receiving complete infusion, partial infusion, infusion paused but resumed for complete infusion, or not infused (comparison by intention-to-treat).
- Number and percentage of participants with infusion-related reactions and symptoms (reported during the infusion or within 2 hours after the infusion), by grade. (Closed report only)
- Number and percentage of participants with an incident AE, SAE, UP or SUSAR on Day 0 during or after the infusion, overall and by oxygen requirement category at time of infusion (oxygen requirement at baseline, unless updated information is available; categories: no supplemental oxygen, < 4 L/min, conventional supplemental oxygen ≥ 4 L/min, high-flow oxygen or mechanical ventilation/ECMO). Types of AEs will be summarized by system organ class and by grade. (Closed report only)

- Number and percentage of participants who received:
 - Prior to infusion, medication to prevent infusion reactions, and type of medication
 - During or within 2 hours after infusion, medication to treat infusion reactions, and type of medication (Closed report only)
- Among participants infused, the day of infusion (same day as randomization, next day, > 1 day after randomization), and time between randomization and beginning of infusion (median hours, IQR).
- Among participants receiving full infusion, duration of infusion (median minutes, IQR).

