 Treatment groups will be compared for new requirements of dialysis, overall and in subgroups by eGFR level (<30 mL/min versus 30 mL/min at study entry), and subgroups by nAb status at study entry (nAb negative or positive).

Motivation: In a joint analysis of data from the first three agents studied in TICO (bamlanivimab, sotrovimab, and BRII 196/198), the incidence of dialysis was elevated in the active treatment group compared with placebo (18 versus 2 events, HR=5.7 [95% CI: 1.2-24.6]). This safety signal was seen only among those who were nAb seronegative at study entry (16 events in the active arms versus 2 placebo, HR=5.0 [95% CI: 1.1 to 22.0]),

while only 2 events occurred among those who were nAb seropositive at study entry, both in the active arms. The mean time from enrollment to needing dialysis was 21 days.

Comment: Of the 20 participants with "incident dialysis", 2 had required dialysis prior to their COVID-19, and thus may be mis-classified for treatment-emergent dialysis. Both had eGFR < 10 mL/min at study entry and thus were at high risk for dialysis, and both had been allocated to active treatment.

Hypothesis: The incidence of dialysis is elevated with nMAb treatment compared with placebo, in particular among those with eGFR < 30 mL/min, and among those who are nAb seronegative at study entry.

- Treatment groups will be compared for mean changes in laboratory test values from baseline to Day 5, and for incidence of grade 3 and 4 laboratory abnormalities at Day 5 (new abnormality or increase in grade). Laboratory tests are conducted locally, and include serum creatinine, AST/SGOT or ALT/SGPT, WBC, hemoglobin, platelet counts, lymphocyte counts, and C-reactive protein. Statistical methods are described in section 3.
- Participants who are pregnant are not eligible for enrolment. For participants who become pregnant, pregnancy outcomes will be summarized.
- In addition to the safety outcomes specified in the platform protocol, other targeted safety outcomes for specific investigational agents may be specified in appendices to the protocol. Analyses will be specified in the corresponding agent-specific appendix to this SAP.

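### SAP Appendix G reports the hypersensitivity AESI through rash only, so non-rash reactions after the 2-hour infusion window are not summarised by arm as the AESI

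*SAP*

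**What the plan says.** - **Protocol H5.5.4** lists two AESIs for MP0420 or placebo: infusion-related reactions and "Allergic/hypersensitivity reactions". It gives no definition, term list or time window for the second.
- **SAP section 7** allows protocol appendices to name further targeted safety outcomes for an agent and says of them: "Analyses will be specified in the corresponding agent-specific appendix to this SAP". For MP0420 that is Appendix G.
- **SAP Appendix G** has a heading on hypersensitivity events of special interest. It was prompted by three healthy volunteers in another study who each had "rash and joint/body pain 10 to 20 days after the single subcutaneous infusion". Cases in this trial come from one search, in which "all participants for whom rash adverse events had been reported through Day 28 were identified". Aches enter through a rash: "Rash events associated with myalgia, arthralgia, or generalized aches and pains will also be summarized by treatment group". The line listing adds "other solicited events that occurred simultaneously". The supplemental Day 28 composite gains rash as its only new component.
- **SAP section 6** covers infusion reactions "reported during the infusion or within 2 hours after the infusion". It also summarises, by system organ class and grade, the "Number and percentage of participants with an incident AE, SAE, UP or SUSAR on Day 0 during or after the infusion".

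**The concern.** The protocol's AESI is a class of reaction; Appendix G's case rule is one sign of it. Anaphylaxis, angioedema or bronchospasm without a rash, arising after the 2-hour window, meets the protocol's wording but not the Appendix G rule. Joint or body pain without rash is also left out, although pain was half of the external picture that led to the Appendix G text.

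At stake is whether the final report can give, by arm, the rate of an AESI that the protocol names. Under the rule as written it can give only the part of that rate that shows as rash.

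**Working it through.** The plan states no figure for this AESI, so there is nothing to reproduce. The check traces where a non-rash hypersensitivity reaction starting after the 2-hour window would appear (SAP sections 2, 6 and 7, Appendices C, D and G).

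| Type of reaction | General output | AESI summary by arm | DSMB listing |
|---|---|---|---|
| SAE, to Day 90 | Composite with SAEs, Day 28 and Day 90 | No | Yes |
| Grade 3-4, non-serious, to Day 28 | Grade 3-4 table by system organ class; Day 28 composite | No | Yes |
| Grade 1-2, non-serious, later on Day 0 | Day 0 table by system organ class and grade | No | No* |
| Grade 1-2, non-serious, present on Days 1-7, 14 or 28 | Any-grade tables by day, grade and system organ class | No | No* |
| Grade 1-2, non-serious, confined to Days 8-13 or 15-27 | Need not be recorded as an adverse event | No | No* |

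*Unless reported as an unanticipated problem.

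**Do the general tables fill the gap?** Only in part. They work by system organ class, and section 7 foresees a split into preferred terms only for classes with a significant treatment difference. Angioedema, bronchospasm, hypotension and arthralgia affect different organ systems, so a few of each would be spread over several rows. Section 7 lets the blinded team build other groupings, but specifies none for hypersensitivity.

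**Counts (Appendix G).**
1. Participants: 485 infused + 11 not infused = 496 randomised; 9 withdrew before infusion + 2 stayed in follow-up = 11. These agree.
2. Rash: 11/485 = 0.0227, or 2.3%, pooled over arms and taking all 11 as infused. The exact 95% interval, from Beta quantiles (0.025; x, n−x+1) and (0.975; x+1, n−x) with x = 11 and n = 485, is 1.1% to 4.0%.
3. External signal: 3/8 = 37.5% at the 400 mg subcutaneous dose, exact 95% interval 8.5% to 75.5%. All three had rash as well as pain.

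**Collection days.** Any-grade events are collected on Days 0-7, 14 and 28. Of the 11 days from Day 10 to Day 20, only Day 14 is among them. This limits mild rash and mild non-rash events alike.

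No input gives the share of hypersensitivity reactions without rash, so the number left out of the AESI count cannot be derived.

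**The case against.** The strongest reply is that Appendix G adds to sections 6 and 7 and does not replace them. A reader might infer from the rash-only rule that late anaphylaxis or angioedema goes uncounted. The documents do not support that: if serious or grade 3-4, it is counted, compared by arm and listed for the DSMB, and milder events present on a collection day reach the general tables. This stands. What is missing is the count as the AESI.

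Three further points have weight.
- Appendix G answers a specific signal, and a rash search would have found all three external cases. That justifies a rash component. It does not justify letting rash stand for the whole AESI, which the SAP dates (Appendix H5, 09 April 2021) about six months before the October 2021 reports.
- The protocol's long list of hypersensitivity signs in H5.1.1 describes immediate, infusion-related reactions. It should not be read as a protocol definition of late reactions. The point rests on H5.5.4, which names the AESI separately and without a time limit.
- Section 7 speaks of outcomes that may be specified, H5.5.4 attaches no analysis, and H5.4.1 refers adverse event assessment and reporting to the master protocol, which is not among the documents. A definition there cannot be excluded, but the SAP points to none.

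It is also tempting to scale up the 11 rash participants by an assumed share of cases without rash. That fails: the 11 had any rash, in either arm, and are not established hypersensitivity cases.

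**Conclusion.** The point holds in a limited form. Appendix G turns a protocol-named AESI into rash, and no specified output gives the AESI by arm for non-rash reactions after the 2-hour window. Those reactions remain visible in the general tables, except that mild, non-serious events between collection days may never be recorded. The grade 1-2 non-serious ones are also absent from the DSMB listings as specified, which matters because the external cases were themselves mild to moderate.

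The size is unknown, and no direction of bias between arms can be claimed, since the same rule applies to both. The conclusion assumes that the master protocol does not define the AESI elsewhere. The change is a cheap improvement to safety reporting; it does not touch the primary analysis.

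**What to change.** Before unblinding, amend Appendix G as follows.
1. Have the blinded team fix a MedDRA term list for hypersensitivity that includes anaphylaxis, angioedema, urticaria and bronchospasm.
2. Apply it to post-infusion adverse events already coded, through Day 28, and to SAEs through Day 90.
3. Tabulate by arm, split into within and after 2 hours of the infusion, with the existing rash summary kept as one component.
4. List these events in the closed report.
5. Show arthralgia or myalgia without rash on a separate supportive line, outside the AESI total, because such aches are non-specific in COVID-19.

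The cost is SAP wording, one blinded review of terms and a query of existing data. Two limits remain. A SAP change cannot recover mild events that fell between collection days. Events exempt from adverse event reporting (SAP Appendix C), such as hypotension needing vasopressors, will be found by the search only if the investigator judged a causal link reasonably possible.

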#### H5.1.1 *Potential benefits and risks from MP0420* Potential benefits

The potent antiviral activity of MP0420 has the potential to reduce the viral load of SARS-CoV-2, which could translate into beneficial clinical effects. This statement is supported by preclinical studies summarized below. MP0420 demonstrated high affinity binding to its target, the RBD in the spike protein of SARS-CoV-2, with no observed off-target binding as measured in Retrogenix assay and GLP TCR study [5]. MP0420 has been shown to potently neutralize SARS-CoV-2 in live virus assays. In addition, several known spike mutations did not affect the antiviral activity of MP0420 in neutralization assays using VSVG-pseudotypes [5, 6]. MP0420 was shown to neutralize variants of the UK originated lineage B.1.1.7 (del69-70, del145, N501Y, A570D, D614G, P681H, T716I, S982A, D1118H) and the South African originated lineage B.1.351 (D80A, D215G, E484K, N501Y, A701V) as efficiently as the wild-type Wuhan virus with IC50 values in the low single-digit ng/mL range. MP0420 also gave potent protection against individual mutations reported in currently circulating SARS-CoV-2 strains: N501Y, E484K, K417E, Y453F, D614G, S477N, A222V, G446V, G476S, T478I, P479S, V483A, Q493K and F490S.

Significant reduction in viral load and pathogenesis was observed in five studies conducted using two hamster models. MP0420 dose-dependently reduced virus titers in the lung, throat and nasal turbinates. Disease-related body weight loss was reduced and a protective effect on lung tissues was observed. Please refer to the IB for details [5].

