interactions between the treatment and subgroup indicators. Subgroup analyses will be performed for time to sustained recovery (primary efficacy outcome) and key safety outcomes, including the composite outcomes of *grade 3 or 4 AEs, SAEs, organ failure, serious infections, or death* through Day 28; *SAEs, organ failure, serious infections, or death* through Day 90. Statistical methods for the subgroup analyses are described in Section 9.1.

Because the composition of the study population may have changed over time, including an increase in the proportion of participants infected with the Delta variant, an increase in the proportion of vaccinated persons in the general population, and changes in the population with respect to supplementary oxygen requirements, models for these subgroup analyses will also consider adjustment for vaccination status, and for supplementary oxygen requirements at study entry (categories of the ordinal pulmonary outcome).

Research Question 2: What is the effect of specific mutations?

AZD7442 is a combination therapy targeting non-overlapping epitopes in the RBD. While mutations found in variants can impact the binding of either one of the nMAbs (including at positions R346, K444, V445, G446, N450, L452 G476, E484, Q493K) the combination is hypothesized to retain activity. Nevertheless, high quality sequencing of the Spike gene will provide information on any relevant RBD mutations that could impact binding of one or both nMAbs.

Hypothesis: The relative benefit of AZD7442 (vs placebo) is larger for those infected with virus without mutations at binding-relevant positions compared with those with such virus mutations.

Statistical Analyses:

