It is expected that the rate of viral variants than contains mutations at the binding-relevant positions is low, with correspondingly low power for statistical tests. For individual mutations that occur at sufficiently high rates, and pooled across mutations, subgroup analyses will be performed comparing AZD7442 versus placebo within subgroups by the presence versus absence of the mutations. The treatment effect will be compared across subgroups by testing for an interaction between the treatment and subgroup indicators. Subgroup analyses will be performed for time to sustained recovery and key safety outcomes, as described above; statistical methods are described in section 8.4 of this SAP. Models will include vaccination status and supplementary oxygen requirements (categories of the ordinal pulmonary outcome) at baseline as covariates.

These are exploratory analyses. In addition, if mutations on other sites occur with sufficient frequency, similar analyses will be performed to identify mutations that are associated with the outcome of the treatment.

E-9 Missing Outcomes and Missing Baseline nAb Status

Missing primary outcome results and 90-day survival status due to withdrawal of consent or loss to follow-up will be summarized by treatment group, and tests will be performed whether the proportion of missing data is independent of the treatment assignment. Baseline factors related to these missing outcome data, overall and for each treatment group, will be determined using logistic regression. Candidate baseline factors for this investigation include, but are not limited to, categories of oxygen requirement (pulmonary outcome), antigen levels, and the disease progression risk score (section 13.2). Summaries of missing outcome data will also include when patients with missing data were last seen and their last known clinical status (e.g., discharged, hospitalized, alive at home).

As sensitivity analyses, multiple imputation may be used to estimate missing outcomes. Other sensitivity analyses may also be considered following unblinding when the final extent of missing data is known and the pattern of missing data is investigated. As of December 28, 2021, 6 participants had withdrawn consent and 23 additional patients had unknown sustained recovery status at 90 days. Follow-up is ongoing, including attempts to reach patients who are lost to follow-up. Thus, these numbers are likely to change.

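### Appendix G carries the AZD7442 mutation list and hypothesis over to MP0420, so the exploratory binding-site subgroup is not defined for MP0420

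*SAP*

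**What the plan says.** The Subgroup Analyses paragraph of SAP Appendix G adds two sets of analyses by cross-reference: "those described in section E-7 (vaccine and immunosuppressive status) and E-8 (viral strain) of Appendix E will be carried out for MP0420". The outcomes are redirected to those in section 9; no position list or hypothesis is given for MP0420.

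Section E-8 has two parts. Research Question 1 compares Delta with other variants. Research Question 2 concerns specific mutations and opens with "AZD7442 is a combination therapy targeting non-overlapping epitopes in the RBD". It then says that mutations "can impact the binding of either one of the nMAbs (including at positions R346, K444, V445, G446, N450, L452 G476, E484, Q493K". Its hypothesis begins "The relative benefit of AZD7442 (vs placebo) is larger for those infected with virus without mutations at binding-relevant positions", and the analysis is set out as follows: "For individual mutations that occur at sufficiently high rates, and pooled across mutations, subgroup analyses will be performed comparing AZD7442 versus placebo". E-8 calls these analyses exploratory and expects few such mutations and low power. It also allows mutations at other sites to be examined if they are frequent enough.

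On the agent itself, protocol section H5.1.1 states that "MP0420 also gave potent protection against individual mutations reported in currently circulating SARS-CoV-2 strains" and lists 14 substitutions.

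**The concern.** Research Question 2 asks whether treatment works less well when the virus is mutated where the drug binds. The answer is interpretable only if the positions are those of the drug being tested. The E-8 list is introduced through its effect on AZD7442: "While mutations found in variants can impact the binding of either one of the nMAbs". MP0420 is a different type of molecule, a DARPin with three domains that bind the receptor-binding domain. Neither document says that the AZD7442 positions matter for its binding.

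If the cross-reference is followed literally, virus is classified by another product's binding sites and the result is reported under MP0420's name. A null interaction would then be weak evidence about MP0420 escape, and a positive one could be misread as resistance to MP0420.

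**Working it through.** No sample size, power or error-rate figure is involved. The check sets the two lists side by side and then looks at how the SAP words its cross-references.

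**Inputs.** The nine positions in SAP E-8, Research Question 2, and the 14 individual substitutions in protocol H5.1.1: N501Y, E484K, K417E, Y453F, D614G, S477N, A222V, G446V, G476S, T478I, P479S, V483A, Q493K, F490S.

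| E-8 entry | Substitution in the protocol's MP0420 list |
|---|---|
| R346 | none |
| K444 | none |
| V445 | none |
| G446 | G446V |
| N450 | none |
| L452 | none |
| G476 | G476S |
| E484 | E484K |
| Q493K | Q493K |

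**Overlap by position.** 4 of 9, and 4 / 9 = 44%. The remaining 9 − 4 = 5 positions do not appear in the protocol at all.

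**Overlap by substitution.** E-8 names a specific substitution only for Q493K, so that is the one exact match (1 of 9). For G446, G476 and E484, E-8 gives the whole position, while the protocol reports a single tested change.

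**Strength of the protocol evidence.** It is laboratory neutralisation. For the individual substitutions it claims potent protection, which is not the same as equality with wild type. E484K has additional support: it is one of the B.1.351 changes, and H5.1.1 says that lineage is neutralised as efficiently as wild type. Section H5.1.2 adds a general expectation that the mutations then current would not reduce potency.

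**Does the SAP justify the transfer elsewhere?** For E-7 it does: that section says its hypotheses, although developed for AZD7442, extend to monoclonal antibodies and antiviral agents in general. E-8 has no such statement. SAP section 1.2 places agent-specific modifications in the agent appendices, and section 1.1 provides for updating the SAP before each agent is unblinded. Appendix G is therefore the natural place for an MP0420 list, and it has none.

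**What the documents cannot supply.** Neither names a position at which MP0420 loses binding, and neither gives mutation frequencies in the MP0420 cohort. The amount of dilution in the pooled comparison cannot be calculated.

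**The case against.** The strongest reply is that E-8 does not fix a closed classifier. Its list is introduced as examples, and the operative idea, positions relevant to binding, could be read functionally and re-applied to MP0420. Individual mutations are to be tested as well as the pooled group, and other sites may be added. On that reading Appendix G is underspecified but not wrong. This softens the point without removing it. The nine positions are the only ones named, and the hypothesis and analysis name AZD7442. Nothing tells the analyst to substitute another list.

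A second reply is that expected retained activity does not make a position unsuitable for testing. E-8 itself expects the AZD7442 pair to keep working despite these mutations and still plans to look. This stands for individual mutations: a null result at E484, for instance, would be a useful clinical check of the laboratory claim. It does not justify pooling such virus into a group meant to represent impaired MP0420 binding.

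A reader might also infer more than the documents support:

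- That 44% of virus or participants would be misclassified. The figure counts listed positions, and no frequencies are given.
- That the protocol shows four positions to be irrelevant to MP0420. It reports one substitution at each, in vitro; other changes at 446, 476 or 484 are not covered.
- That the interaction test would be uninformative. It would say little about escape when pooled, but the individual-mutation analyses keep some value.

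**Conclusion.** The point holds as a specification error of limited reach. Read literally, Appendix G pre-specifies for MP0420 a pooled binding-site subgroup and a directional hypothesis that belong to another product. At four of the nine positions the protocol reports potent MP0420 protection against a tested substitution, and at the other five it reports nothing.

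A reader might infer a threat to the trial's conclusions; the documents do not support that. The primary and key secondary analyses and the monitoring rules do not use Research Question 2. SAP section 9.1 already says that subgroup results are unadjusted for multiplicity and need caution. Research Question 1 is unaffected in its grouping, because Delta versus other does not depend on the agent.

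The conclusion assumes that the reference to E-8 covers the whole section. Its viral-strain label could be taken to mean only the Delta comparison, but that is the heading over both research questions. If only the first was intended, one clarifying sentence settles the matter.

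**What to change.** Amend Appendix G before MP0420 results are unblinded, in one of two ways.

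(a) Replace the E-8 list and hypothesis with MP0420-specific binding-relevant mutations taken from the sponsor's own neutralisation data. Define them by substitution where the data are substitution-specific. Keep substitutions with tested retained potency out of the pooled mutation-present group, but allow them to be analysed individually.

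(b) If no such list exists, limit the import to Research Question 1, reworded for MP0420, and label any mutation-level analysis as hypothesis-generating, without reference to the AZD7442 positions.

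Option (b) costs a sentence or two and needs no new data. Option (a) costs a short list and a restated hypothesis, provided that the sponsor holds suitable data; the two documents do not show whether it does. Neither option changes data collection or sample size.
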